### ***Secondary outcomes***

The following secondary outcomes will all be compared by chi-square test.

- The proportion of patients with specialist referral or further liver assessments, regardless of fibrosis score results, is calculated as the number of patients with specialist referral or further liver assessments divided by the total number of patients.
- Among patients with low fibrosis scores, the proportion of patients with inappropriate specialist referrals is calculated as the number of patients referred for specialist care divided by the total number of patients.
- The proportion of patients with confirmed advanced fibrosis is calculated as the number of patients with confirmed advanced fibrosis divided by the total number of patients.

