### **3. STUDY DESIGN OVERVIEW**

This will be a parallel group, randomized controlled trial (Figure 1). Patients fulfilling the inclusion and exclusion criteria above will be randomized 1:1 to two groups. Randomization will be carried out through the use of computer-generated list of random numbers in variable blocks of 4 to 10. Concealment of group allocation will be achieved through putting the group allocation cards in consecutively-numbered and sealed envelopes. The patients and physicians will know that the patients are in the intervention group if they see the reminder messages. When they do not see a reminder message, there will not be a specific indicator of whether the patient is in the control group or in the intervention group but having low fibrosis scores. Furthermore, the outcome assessors will be blinded to the group assignment.

For patients in the intervention group, we will calculate the fibrosis scores. For patients with increased fibrosis scores, we will type the following pop-up message in our electronic clinical management system:

*“This patient has high Fibrosis-4 index (and/or AST-to-platelet ratio index) of xxx suggestive of significant liver fibrosis. Please consider referring the patient to the hepatology clinic or arranging further test such as FibroScan.”*

The reminder message will pop up when physicians see the patient at the clinic and use the electronic clinical management system. The message will remain active for one year. Although the message is entered manually at this stage, the arrangement mimics an automated computer system. If the study results are positive, the next step is to modify the system to automate the process.

Patients in the control group will undergo the same assessments as patients in the intervention group. Although physicians will have access to the raw liver biochemistry results and platelet count, the fibrosis score results will not be specifically shown, and there will be no electronic reminder messages regardless of the fibrosis scores. This is to mimic usual care when there is no dedicated care model for case identification.

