### **4.2 Exclusion criteria**

Subjects having any of the following will be excluded from the study:

- Type 1 diabetes
- Already receiving specialist care by gastroenterologists or hepatologists
- Current or past history of hepatocellular carcinoma or liver decompensation
- Active malignancies other than hepatocellular carcinoma, unless in complete remission for more than 5 years

Notably, although our primary focus is to identify patients with NAFLD and advanced liver fibrosis, we will not exclude patients with other chronic liver diseases such as chronic viral hepatitis or alcohol-related liver disease. In real life, although NAFLD is the most common chronic liver disease among diabetic patients, they can also have other liver diseases. It would also be meaningful to detect those diseases, especially if advanced fibrosis has already developed.

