## **6.2 Secondary outcomes**

The following secondary outcomes will be analyzed:

- The proportion of patients referred for specialist care or further liver assessments, regardless of fibrosis score results.

- The proportion of patients with low fibrosis scores who are referred for specialist care. Because NAFLD is highly prevalent and only a minority of patients have advanced fibrosis, referral of patients who will unlikely develop liver-related complications to specialists represents inefficient use of precious healthcare resource and should be minimized. This notion has major resource implications, and the current study will provide important information to guide healthcare policy. We recognize that physicians may have other reasons to refer patients for specialist care (e.g. newly diagnosed viral hepatitis). The reasons for referral will be recorded and reported.
- The proportion of patients confirmed to have advanced fibrosis. In this study, a patient is considered to have confirmed advanced fibrosis if (1) liver stiffness measurement by transient elastography is >15 kPa [22], (2) a liver biopsy shows bridging fibrosis (F3) or cirrhosis (F4), (3) unequivocal radiological features of cirrhosis (cirrhosis with nodular appearance, splenomegaly, ascites or varices), or (4) clinical, radiological or endoscopic evidence of portal hypertension. In case of discrepant results, liver biopsy and unequivocal evidence of cirrhosis and/or portal hypertension will override the liver stiffness measurement results.

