### **6.4 Statistical analysis**

We will perform intention-to-treat analysis for all primary and secondary outcomes. All randomized patients will be analyzed for the outcomes. Patients who are lost to follow-up will be considered not to have specialist referral, further liver assessments, and confirmed advanced fibrosis. Statistical significance is taken as a two-sided p value of <0.05.

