#### ***Primary outcome***

The primary outcome includes patients with high fibrosis scores in both groups and is calculated as the number of patients with specialist referral or further liver assessments divided by the total number of patients. The proportions in the two study groups will be compared by chi-square test.

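### The all-patient referral outcome is compared by a valid but unstratified chi-square test; stratifying by baseline fibrosis score would give a modest precision gain whose size depends on an unstated low-score referral rate

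*Combined protocol and SAP*

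**What the plan says.** Section 6.4 of the combined protocol and SAP, under Secondary outcomes, states: "The following secondary outcomes will all be compared by chi-square test". One of these outcomes is the proportion of all patients, whatever their score, with specialist referral or further liver assessment. No strata or covariates are named there, and section 3 describes randomisation in variable blocks without strata. Section 6.4 sets a two-sided 5% threshold but specifies no confidence interval.

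Three other statements bear on the point:
- **Who gets the reminder.** Section 3: "For patients with increased fibrosis scores, we will type the following pop-up message in our electronic clinical management system".
- **Score status in both arms.** Section 3: "Patients in the control group will undergo the same assessments as patients in the intervention group". Section 6.4 then uses the score to define two other analyses: "The primary outcome includes patients with high fibrosis scores in both groups", and, for a secondary outcome, "Among patients with low fibrosis scores, the proportion of patients with inappropriate specialist referrals".
- **Analysis set.** Section 6.4: "All randomized patients will be analyzed for the outcomes". Patients lost to follow-up count as not referred.

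**The concern.** The reminder can act directly only on high scorers, who are 25% of the sample on the planning figure in section 6.5, or 33% on its preliminary FIB-4 figure. The other 75% or 67% are expected to have the same referral rate in both arms. If that rate differs from the rate in high scorers, chance imbalance between arms in the share of high scorers adds noise to the pooled comparison. A stratified analysis removes most of this noise using a baseline variable the trial must derive anyway. At stake is how precisely the all-patient effect of the care model is estimated.

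**Working it through.** **1. The plan's own figure.** Section 6.5 assumes 20% versus 37%, two-sided 5%, 80% power. With unpooled variance, n = (1.960 + 0.842)² × (0.20×0.80 + 0.37×0.63) / 0.17² = 106.8, so 107 per group. Then 2 × 107 / 0.25 = 856, and 856 / 0.9 = 951.1, which becomes 952 (476 per arm). All three figures reproduce. They concern the primary outcome; the documents size nothing for the all-patient outcome.

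**2. Inputs for the check.**
- N = 476 per arm and high-score share f = 0.25 (section 6.5).
- High-score rates after counting 10% as lost and not referred: a = 0.9 × 0.20 = 0.180 and b = 0.9 × 0.37 = 0.333.
- Low-score referral rate q: not in the documents. I assume 0% to 20%, equal in both arms, diluted to l = 0.9q.

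**3. Formulas.** The overall rates are pc = f·a + (1−f)·l and pt = f·b + (1−f)·l.
- Unstratified variance: U/N, with U = pc(1−pc) + pt(1−pt).
- Stratified variance with the high-score share treated as fixed: S/N, with S = f[a(1−a) + b(1−b)] + 2(1−f)·l(1−l).
- Extra term because the share is random and the effect differs by stratum: H/N, with H = (b−a)²·f(1−f)/2 = 0.153² × 0.1875 / 2 = 0.0022.

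**4. One case in full (q = 0%).** pc = 0.0450 and pt = 0.08325, so U = 0.0430 + 0.0763 = 0.1193 and SD = √(0.1193/476) = 1.58 points. S = 0.25 × (0.1476 + 0.2221) = 0.0924. S + H = 0.0946, so SD = 1.41 points. The reduction is 1 − 1.410/1.583 = 10.9%.

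**5. Across the range (25% high scores).**

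| Assumed low-score rate | U | S + H | SD, unstratified → stratified (points) | Reduction |
|---|---|---|---|---|
| 0% | 0.1193 | 0.0946 | 1.58 → 1.41 | 10.9% |
| 2% | 0.1425 | 0.1211 | 1.73 → 1.60 | 7.8% |
| 5% | 0.1759 | 0.1591 | 1.92 → 1.83 | 4.9% |
| 10% | 0.2279 | 0.2175 | 2.19 → 2.14 | 2.3% |
| 20% | 0.3182 | 0.3160 | 2.59 → 2.58 | 0.3% |

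With 33% high scores the same formulas give reductions of 10.0%, 7.5%, 5.0%, 2.5% and 0.4%.

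**6. Simulation (200,000 trials per setting, 25% high scores).** The simulated SDs agree with the table to within 0.01 point. Power, chi-square to Cochran-Mantel-Haenszel, is 68.0 to 77.4% at 0%, 60.2 to 66.9% at 2%, 51.0 to 55.2% at 5%, 41.8 to 43.1% at 10%, and 31.5 to 31.5% at 20%. Type I error is 4.9–5.1% for both tests. The mean risk difference is the same (3.82 versus 3.81 points; expected value 0.25 × 0.153 = 3.83).

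**7. The 0% row is not new evidence.** With no low-score referrals, the stratified test depends only on high scorers. Its simulated power is 77.5%, against 77.6% for the primary test in a like run. Over all the low-score rates tried, the all-patient outcome is significant while the primary is not in at most 2.6% of trials, with either test.

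**8. The interval.** A Mantel-Haenszel interval that leaves out H is slightly too narrow. At 0% its simulated coverage is about 94.5%, and its mean width suggests a 12% gain where the true SD gain is 11%. Including H raised coverage to 94.8% and widened the mean interval from 5.43 to 5.50 points.

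**The case against.** The strongest reply is that nothing is wrong. A chi-square test on an all-patient secondary outcome is standard and valid, and the trial is sized only on high scorers. A more efficient test is then a matter of preference. That stands, and it limits the point to an optional improvement.

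The second reply is that the documents cannot show that a material gain exists. They give no low-score referral rate, and two statements suggest it may not be near zero. On eligibility, section 4.2 says "we will not exclude patients with other chronic liver diseases such as chronic viral hepatitis or alcohol-related liver disease". On referral, section 6.2 says "We recognize that physicians may have other reasons to refer patients for specialist care (e.g. newly diagnosed viral hepatitis". This also stands. At 10% the gain is about 2% of the SD, and at 20% it is practically nil.

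A reader might infer more than the documents support:
- *That the plan's test is biased or has the wrong error rate.* It does not: type I error and the mean difference are unaffected.
- *That about nine points of power are being lost.* That holds only at a 0% low-score rate, where the stratified test in effect repeats the primary.
- *That the planned interval is too wide.* The plan specifies no interval.
- *That the change is free.* The simple fixed-share interval under-covers slightly, and unscored patients need a stratum of their own.

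What survives is that the stratifying variable is already required, the target risk difference is unchanged, and no power was lost beyond simulation error where there was no gain.

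**Conclusion.** The point holds as a modest, optional efficiency gain on one secondary outcome. The SD of the all-patient risk difference would fall by about 11% at best, about 5% at a 5% low-score referral rate, and 2% or less from 10% upward. This rests on the section 6.5 rates, 10% loss counted as not referred, and an equal low-score rate in both arms. Equality is my assumption; it is reasonable because low scorers receive no reminder. The low-score rate itself is unknown. The benefit is a more precise all-patient estimate. It is not additional evidence of efficacy, since the expected effect lies in the high scorers, whom the primary analysis already covers. The primary analysis is unaffected.

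**What to change.** Before any comparison by arm, amend section 6.4 for this outcome only:
- Replace the chi-square test with a Cochran-Mantel-Haenszel test stratified by baseline score: high (by the same rule that triggers the reminder), low, or not calculable. The third stratum keeps every randomised patient in the analysis.
- Report a Mantel-Haenszel risk difference with a 95% confidence interval, using a variance that includes the random-share term. A common odds ratio would be a different estimand, because the effect is expected in one stratum only.

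The cost is a few lines of SAP text and code, with no new data or patients. The third stratum is of unknown size. In section 6.6, 612 − 599 = 13 patients (2.1%) lacked complete laboratory data, but that count also covered the NAFLD fibrosis score. If 2.1% were unscored, about 20 of 952 patients would be affected; with that stratum added, simulated power still rose from 49.6% to 53.6% at a 5% low-score rate. If low-score referral is 10–20% or more, the change gains little or nothing. The same reasoning could be applied to confirmed advanced fibrosis, but the documents give no rates by score from which to size a gain, so no change is proposed there.

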### **1.3 Non-invasive prediction of advanced fibrosis by prediction scores**

The severity of liver fibrosis is a key determinant of liver-related morbidity and mortality in NAFLD patients. In a meta-analysis of 1495 biopsy-proven NAFLD patients from 5 studies, the incidence of all-cause mortality was increased by 3.5-fold and 6.4-fold in patients with bridging fibrosis (F3) and cirrhosis (F4), respectively, compared with those without fibrosis [10]. It is therefore important to identify patients with advanced fibrosis for further monitoring and management. Although we demonstrated the role of transient elastography screening in patients with type 2 diabetes [9], the number of diabetic patients exceeds the capacity of most medical centers. Besides, since diabetic patients can develop many other complications, it is important to keep the diagnostic and referral process simple.

Using liver histology as the reference standard, various groups have derived and validated

simple scores to predict advanced liver fibrosis [11]. These scores are calculated from routine clinical and laboratory parameters and have high applicability in different clinical settings. Although the scores are not as accurate as transient elastography or magnetic resonance elastography, they have high negative predictive values in excluding advanced fibrosis and are well suited for initial assessment [12, 13]. In our own study, the area under the receiver-operating characteristics curve for detecting advanced fibrosis (F3-4) and cirrhosis (F4) was 0.74 and 0.75 for the aspartate aminotransferase-to-platelet ratio index (APRI), 0.80 and 0.81 for the Fibrosis-4 (FIB-4) index, and 0.75 and 0.80 for the NAFLD fibrosis score, respectively [13]. Importantly, patients with low fibrosis scores have very low risk of developing liver-related morbidity and mortality during long-term follow-up [14, 15].

Among the published simple scores, the FIB-4 index and NAFLD fibrosis score have been consistently shown to be the most accurate in detecting advanced fibrosis by our group and others [12, 13]. We select the FIB-4 index and APRI as initial assessment in this study because we found that the NAFLD fibrosis score is increased in the majority of diabetic patients and is indiscriminating in this population (please see section on Preliminary Data for details).

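### Section 6.4 labels every specialist referral of a low-score patient inappropriate, although sections 6.2 and 4.2 recognise valid reasons for such referrals

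*Combined protocol and SAP*

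**What the plan says.** Section 6.2 lists as a secondary outcome: "The proportion of patients with low fibrosis scores who are referred for specialist care". The reason given is that "referral of patients who will unlikely develop liver-related complications to specialists represents inefficient use of precious healthcare resource and should be minimized". It then accepts that physicians may refer for other reasons, with newly diagnosed viral hepatitis as its example, and adds: "The reasons for referral will be recorded and reported".

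Section 6.4 (Secondary outcomes) gives the calculation for the same outcome among low-score patients: "the proportion of patients with inappropriate specialist referrals is calculated as the number of patients referred for specialist care", over all low-score patients, compared by chi-square test.

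Section 4.2 states that "we will not exclude patients with other chronic liver diseases such as chronic viral hepatitis or alcohol-related liver disease", and says that finding those diseases is also worthwhile, above all when fibrosis is already advanced.

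The primary outcome (6.1) and the all-patient secondary outcome (6.2) count either specialist referral or a further liver assessment. The low-score outcome counts specialist referral only. Section 6.3 has two blinded researchers look for both kinds of event in the records of all patients.

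**The concern.** Sections 6.2 and 6.4 use the same numerator but give it different meanings. In 6.2 it is a neutral count of referrals, to be read alongside their reasons. In 6.4 it is a count of inappropriate referrals, with no step that judges whether a given referral was inappropriate. A low-score patient referred because hepatitis was newly found would appear in the inappropriate rate, although 6.2 accepts that reason and 4.2 regards finding such disease as worthwhile.

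Section 6.2 says that this result should inform health policy, so readers may take the rate at face value. If the reasons are first used to separate valid from inappropriate referrals after the results are known, that classification will be post hoc.

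**Working it through.** **1. The plan's own figures.** Section 6.5 gives no rate, power or sample size for the low-score outcome. Its figures serve here only to size the low-score group, and they reproduce:
- Per group, unpooled variance: (1.960 + 0.842)² × (0.20 × 0.80 + 0.37 × 0.63) / 0.17² = 106.8, so 107 as stated. The pooled formula gives 110.
- Total: 2 × 107 / 0.25 = 856. With 10% dropout, 856 / 0.90 = 951.1, so 952, or 476 per arm.

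**2. Expected low-score patients per arm.**
- At 25% with high scores (the planning value): 476 × 0.75 = 357, of which 1% is 3.6.
- At 33% (the preliminary figure for FIB-4 alone): 476 × 0.67 = 319, of which 1% is 3.2.

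**3. Size of the overstatement.** Let r be the proportion of low-score patients referred to a specialist, and q the share of those referrals made for another valid liver indication. Section 6.4 reports r. The rate that fits the label is r × (1 − q). The excess is r × q. The documents give neither r nor q. The values below are assumptions, with r from 2% to 10% and q from 0 to 50%, on 357 patients per arm:

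| r | q | Counted in 6.4 | Fitting the label | Excess |
|---|---|---|---|---|
| any | 0 | r × 357 | r × 357 | 0 |
| 2% | 50% | 7.1 | 3.6 | 3.6 |
| 5% | 30% | 17.9 | 12.5 | 5.4 |
| 10% | 50% | 35.7 | 17.9 | 17.9 |

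The excess runs from nothing to 5 percentage points. It cannot be negative, because the label can only be too broad.

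**4. Comparison between arms.** Under section 3, the reminder is entered only for intervention patients with raised scores. Low-score patients receive no message in either arm, and nothing specific shows the physician which arm they are in. Referrals for other reasons should therefore be balanced by randomization. The absolute level is affected; no bias between arms follows.

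**5. Whether a planned outcome shows direct testing in low-score patients.** The all-patient composite includes those tests but mixes them with the intended effect. On the section 6.5 assumptions, that effect alone raises the composite by 0.25 × (37 − 20) = 4.25 percentage points, with no change in low-score patients. A rise in the composite therefore cannot be read as over-testing.

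**The case against.** The strongest defence is that the numerator is sound and only one word is wrong. Counting all referrals is objective and avoids judging each physician's motive. Section 6.2 already promises the reasons, so a reader of the report could see which referrals had another cause. This stands as a defence of the count. It does not defend the label, since nothing in the plan links the recorded reasons to the rate that 6.4 calls inappropriate.

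A reader might go further and infer that the outcome mismeasures resource use because it omits low-score patients sent directly for FibroScan or another liver test. The documents do not support that. The target stated in 6.2 is referral to specialists, and the numerator counts exactly that. The remark in section 1.3 that "the number of diabetic patients exceeds the capacity of most medical centers" explains why simple scores should come before elastography; it does not make direct testing the target of this outcome. Direct tests are also collected in all patients under 6.3, and the low-score composite could be obtained by subtracting the high-score count from the all-patient count. Omitting them narrows the picture of resource use. It is not an error in the stated outcome.

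Nor can the documents show whether a broader measure would come out higher or lower. With the ranges above and an assumed 0 to 10% sent only for a direct test, the ratio of a broader, reason-adjusted count to the count in 6.4 runs from 0.5 (2% referred, half for other reasons, no direct tests) to 6 (2% referred, none for other reasons, 10% tested: 12 / 2). Even that treats every direct test as unnecessary, and the plan does not say that reasons for direct tests are recorded.

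**Conclusion.** The inconsistency is real and limited. Section 6.4 attaches a judgement to a count that section 6.2 leaves neutral, and the inappropriate rate is overstated by any referral made for another valid liver indication. The size is unknown: about 3.6 patients per arm for each 1% of 357, or 3.2 for each 1% of 319. The 357 rests on the planning assumption of 25% with high scores and on 476 randomized per arm.

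The absence of direct tests is a separate and lesser matter: a useful addition, not a correction. The primary outcome and the sample size do not depend on this outcome, and no bias between arms is shown. The change is still worth making before analysis, because the outcome is meant for policy use and the remedy is cheap.

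**What to change.** **Align section 6.4 with section 6.2, in one of two ways:**
- Rename the outcome *specialist referrals in low-score patients* and keep the numerator. This needs wording only.
- Or keep the word inappropriate and count only referrals whose recorded reason is not another valid liver indication. Fix the categories of reason before the results are seen, have the reasons classified blind to arm, and tabulate the remaining referrals separately. Blinding is practicable because low-score patients have no reminder in either arm.

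**In addition,** report by arm the proportion of low-score patients with specialist referral or a further liver assessment, with the two components shown separately. Section 6.3 already collects both. Describe this as a broader view of resource use, and do not call direct tests unnecessary unless their reasons are recorded too, which would be a new data item.

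**Cost:** a small amount of blinded classification under the second option, and one more secondary comparison. No change to recruitment, sample size or the primary analysis.

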## **4. PATIENTS**

We will recruit consecutive subjects from the Diabetes Mellitus and Endocrine Centre, Prince of Wales Hospital when they attend for diabetes complications screening.

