# **6. DATA ANALYSIS**

## **6.1 Primary outcome**

The primary outcome is the proportion of patients with high fibrosis scores who are referred for specialist care or further liver assessments within 1 year of the baseline visit. In this study, appropriate further liver assessments for advanced liver disease include transient elastography (FibroScan), shear wave elastography, acoustic radiation force impulse, magnetic resonance elastography, liver biopsy, and specific blood biomarkers of liver fibrosis such as FibroTest and FibroMeter. This primary outcome will address our primary aim to evaluate whether a care model comprising fibrosis score testing and electronic reminder messages can increase case identification and improve the diagnostic process.

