### **6.3 Outcome ascertainment**

Two researchers will review the clinical records of all patients for evidence of specialist referral or arrangement of further liver assessments. They will also use the electronic clinical management system to look for new specialist clinic appointments and radiological test arrangements. The researchers will be blinded to the group assignment. In case of discrepant interpretation, a third assessor will study the case and discuss with the other two assessors to come up with a consensus on whether a patient has specialist referral, further liver assessments, and advanced fibrosis.

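### Do the secondary outcomes need their own time window, given that the reminder lapses at one year?

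*Combined protocol and SAP*

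**What the plan says.** Only the primary outcome has an explicit window: section 6.1 counts patients "referred for specialist care or further liver assessments within 1 year of the baseline visit". In 6.2 the first secondary outcome is "The proportion of patients referred for specialist care or further liver assessments, regardless of fibrosis score results", with no limit. The low-score referral outcome has none either. For the third, "a patient is considered to have confirmed advanced fibrosis if (1) liver stiffness measurement by transient elastography is >15 kPa", or if biopsy, imaging or portal hypertension criteria are met; no date is given by which this must happen. Section 6.4 defines its proportion as the "number of patients with confirmed advanced fibrosis divided by the total number of patients".

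On ascertainment, 6.3 states: "Two researchers will review the clinical records of all patients for evidence of specialist referral or arrangement of further liver assessments". It gives no review date. Section 6.4 adds: "Patients who are lost to follow-up will be considered not to have specialist referral, further liver assessments, and confirmed advanced fibrosis".

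Four places refer to one year:
- Section 3, on the reminder: "The message will remain active for one year".
- Section 6.1, as quoted above.
- Section 6.5, which defends the dropout rate by saying that referral and linkage to care are observed over one year.
- Section 8, which ends adverse event reporting after one year of follow-up.

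Section 5.3 allows up to 12 weeks between referral and the hepatology clinic visit, where elastography is done and biopsy may be discussed.

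**The concern.** The intervention switches off. After one year a referral in either arm is usual care. Entry is staggered, since section 4 says "We will recruit consecutive subjects from the Diabetes Mellitus and Endocrine Centre", so a single review date would give early recruits extra time without the reminder. Those later referrals would fall more heavily in the control arm, where fewer patients have already been referred, and would pull the ratio towards 1.

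A strict one-year close has the opposite difficulty. A patient referred in week 50 may not be seen until week 62, and would stay in the denominator as not confirmed. The rule on loss to follow-up also presupposes an end of follow-up, which is not written down for confirmed fibrosis.

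At stake is the secondary aim in section 2, which is tested on confirmed advanced fibrosis. If the answer depended on a review date chosen after data had accrued, that would be a weakness.

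**Working it through.** **The plan's own figure.** Inputs from 6.5: 20% v 37% referred among high scorers, 5% significance level (two-sided, 6.4), 80% power. With unpooled variance, n = (1.960 + 0.842)² × (0.20×0.80 + 0.37×0.63) / 0.17² = 106.8, so 107 per group. Then 2 × 107 / 0.25 = 856, and 856 / 0.90 = 951.1, so 952. The sample size reproduces and does not involve the secondary outcomes.

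**Model for confirmed fibrosis.** From the plan: 476 per arm, 25% with high scores, 20% v 37% referred in year 1. Assumed, because the documents do not say: referrals spread evenly over 52 weeks; 30% of referred high scorers confirmed; no dropout; no cases from other routes; a fixed wait w to the clinic; and, where needed, even recruitment over 52 weeks and a yearly referral rate r among those not yet referred once the reminder has lapsed.

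Cumulative referral is G(t) = p·t/52 up to week 52, and 1 − (1 − p)(1 − r)^((t−52)/52) afterwards. Expected cases = 476 × 0.25 × 0.30 × G(F − w) = 35.7 × G(F − w), where F is the end of record reading, averaged over patients if F varies. Power uses the pooled normal formula for two proportions, 476 per arm.

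**Benchmark: every year-1 referral fully worked up.** 35.7 × 0.20 = 7.14 v 35.7 × 0.37 = 13.21 cases; ratio 1.85; difference 6.07/476 = 1.275 points; power 27.4%.

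**Each patient read to one year (F = 52).** The share of clinic referrals first seen after closure is w/52.

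| Wait | Seen after closure | Cases | Ratio | Power |
|---|---|---|---|---|
| 2 weeks | 4% | 6.87 v 12.70 | 1.85 | 26.5% |
| 6 weeks | 12% | 6.32 v 11.68 | 1.85 | 24.7% |
| 12 weeks | 23% | 5.49 v 10.16 | 1.85 | 22.0% |

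The same fraction is lost in both arms, so the ratio does not move. Biopsy time would add to the loss; referral early in the year would reduce it.

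**All records read to one date (F = 52 + Uniform(0, 52), w = 6).**

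| r, control / intervention | Cases | Ratio | Difference (points) | Power |
|---|---|---|---|---|
| 0% / 0% | 7.09 v 13.12 | 1.85 | 1.27 | 27.3% |
| 10% / 10% | 8.23 v 14.02 | 1.70 | 1.22 | 23.6% |
| 20% / 20% | 9.43 v 14.96 | 1.59 | 1.16 | 20.4% |
| 20% / 30% | 9.43 v 15.95 | 1.69 | 1.37 | 25.9% |
| 10% / 20% | 8.23 v 14.96 | 1.82 | 1.41 | 29.2% |

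The ratio falls whenever r is above zero in these rows. The absolute difference shrinks only when the arms have equal rates after the lapse; with some carry-over in the intervention arm it rises.

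**A fixed cut-off at 52 + 12 = 64 weeks, r = 20% in both arms, against a one-year close.**

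| Wait | Ratio at 64 weeks | Power at 64 weeks | Power at 52 weeks |
|---|---|---|---|
| 2 weeks | 1.70 | 23.6% | 26.5% |
| 6 weeks | 1.75 | 25.0% | 24.7% |
| 12 weeks | 1.85 | 27.4% | 22.0% |

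The later cut-off does better only if waits are long or few referrals follow the lapse.

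**Low-score referrals.** Under section 3 these patients receive no reminder in either arm, so longer follow-up raises both proportions and no dilution is expected.

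**The case for a change.** The best case for a change is that none of the one-year statements is an outcome definition for confirmed fibrosis. Section 6.5 is defending a dropout rate and section 8 concerns safety. Neither says by when fibrosis must be confirmed, and confirmation necessarily lags referral. If one review date were used, recruitment lasted 104 weeks and both arms had a 20% yearly rate after the lapse, the ratio would fall to about 1.41 and power to 15%. A few sentences would remove any choice of date after data accrue, at little cost.

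Part of this stands. The confirmation date is not stated, and a one-year close would count some late work-ups as not confirmed. The large losses, however, rest on a single review date that no section describes, and on post-reminder rates and a recruitment length that the documents do not give. The silence in 6.4 is weak evidence for that reading: the same section restates the primary outcome without its one-year limit too, because it sets out numerators and denominators and leaves windows to the definitions. The first secondary outcome is the primary event extended to all patients, so the window in 6.1 carries over naturally.

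**Conclusion.** No change to the plan is called for. The secondary outcomes do lack a written window, but the surrounding text points consistently to one year from baseline, and an analyst would apply that to both arms alike. Randomisation in blocks keeps follow-up length balanced, so neither reading biases the comparison between arms; the choice affects only which effect is estimated and how many events are counted.

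On the one-year reading the ratio stays at 1.85 and power for confirmed fibrosis falls from 27% to between 26% and 22% for waits of 2 to 12 weeks. That test is weak under every reading because only about 7 v 13 cases are expected, and no window cures this. A 64-week cut-off is a fair alternative, not a clear improvement. These sizes rest on the assumed 30% yield, even referral timing and fixed waits; the ratios do not depend on the yield. The primary outcome and the sample size are unaffected.
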